7.7 Investigational Product

7.7.1 Ixazomib Preparation, Reconstitution, and Dispensing

Ixazomib is an anticancer drug and as with other potentially toxic compounds caution should be exercised when handling ixazomib capsules.

7.7.1.1 Ixazomib Packaging and Labeling

The study drug ixazomib capsules will be provided by Millennium. The study drug will be labeled and handled as open-label material, and packaging labels will fulfill all requirements specified by governing regulations.

The capsules are individually packaged using cold-form foil-foil blisters that are in a child-resistant carton. There are 3 capsules in each wallet/carton.

7.7.1.2 Ixazomib Storage, Handling, and Accountability

Upon receipt at the investigative site, ixazomib should remain in the blister and carton provided until use or until drug is dispensed. The container should be stored at the investigative site refrigerated (36°F to 46°F, 2°C to 8°C). Ensure that the drug is used before the retest expiry date

provided by Millennium. Expiry extensions will be communicated accordingly with updated documentation to support the extended shelf life.

In countries where local regulations permit, ixazomib capsules dispensed to the patient for take-home dosing should remain in the blister packaging and refrigerated as noted above until the point of use. The investigative site is responsible for providing the medication to the patient in the correct daily dose configurations. Comprehensive instructions should be provided to the patient in order to ensure compliance with dosing procedures. Patients who are receiving take-home medication should be given only 1 cycle of medication at a time. Patients should be instructed to store the medication refrigerated (36°F to 46°F, 2°C to 8°C) for the duration of each cycle. Patients should be instructed to return their empty blister packs to the investigative site, rather than discarding them. Reconciliation will occur accordingly when the patient returns for their next cycle of take-home medication. Any extreme in temperature should be reported as an excursion and should be dealt with on a case-by-case basis.

Because ixazomib is an investigational agent, it should be handled with due care. Patients should be instructed not to chew, break, or open capsules. In case of contact with broken capsules, raising dust should be avoided during the clean-up operation. The product may be harmful by inhalation, ingestion, or skin absorption. Gloves and protective clothing should be worn during cleanup and return of broken capsules and powder to minimize skin contact.

The area should be ventilated and the site washed with soap and water after material pick-up is complete. The material should be disposed of as hazardous medical waste in compliance with federal, state, and local regulations.

In case of contact with the powder (e.g., from a broken capsule), skin should be washed immediately with soap and copious amounts of water for at least 15 minutes. In case of contact with the eyes, copious amounts of water should be used to flush the eyes for at least 15 minutes. Medical personnel should be notified. Patients are to be instructed on proper storage, accountability, and administration of ixazomib, including that ixazomib is to be taken as intact capsules.

After cycle 1 and with approval of the treating investigator, subjects may take ixazomib at home. Research center personnel will review the dosing instructions with subjects. Subjects will be asked to maintain a diary to record drug administration. Subjects will be asked to bring any unused drug and empty drug containers to the research center at their next visit. Research personnel will count and record the number of used and unused drug at each visit and reconcile with the patient diary.

7.7.2 Lenalidomide

7.7.2.1 Lenalidomide Dispensing

Commercially available (lenalidomide) capsules are supplied through the lenalidomide REMS® program as the drug is approved for indications in this study. Lenalidomide is for PO (oral) administration only.

Lenalidomide will be provided in accordance with the lenalidomide REMS® program of Celgene Corporation. Per standard lenalidomide REMS® requirements, all physicians who prescribe lenalidomide for research subjects enrolled into this trial must be registered in and must comply with all requirements of the lenalidomide REMS® program. Prescriptions must be filled within 7 days. Only enough lenalidomide for one cycle of therapy will be supplied to the patient each cycle. Unused lenalidomide will be counted and documented by each site. See appendix 14.7 for lenalidomide Prescribing Information.

7.7.2.2 Lenalidomide Storage, Handling and Accountability

Store lenalidomide at 25°C (77 °F) away from direct sunlight; excursions permitted to 15-30°C (59-86 °F). Bottles of lenalidomide will contain a sufficient number of capsules to last for one cycle of dosing. Sites will be required to record and document subject compliance regarding lenalidomide dosing.

Research center personnel will review the dosing instructions with subjects. Subjects will be asked to maintain a diary to record drug administration. Subjects will be asked to bring any unused drug and empty drug containers to the research center at their next visit. Research personnel will count and record the number of used and unused drug at each visit and reconcile with the patient diary.

7.7.3 Dexamethasone

Dexamethasone, a synthetic adrenocortical steroid, is a white to practically white, odorless, crystalline powder. It is stable in air. It is practically insoluble in water.

7.7.3.1 Dexamethasone Dispensing

Dexamethasone is a commercially available PO drug, supplied as 2 and 4 mg tablets.

7.7.3.2 Dexamethasone Storage, Handling and Accountability

Store dexamethasone at controlled room temperature 20°C to 25°C (68°F to 77°F). Sites will be required to record and document subject compliance regarding dexamethasone dosing. Subjects may take oral dexamethasone at home. Research center personnel will review the dosing instructions with subjects. Subjects will be asked to maintain a diary to record drug administration.

7.8 Study Compliance

Study drug will be administered or dispensed only to eligible patients under the supervision of the investigator or identified sub-investigator(s). The appropriate study personnel will maintain records of study drug receipt and dispensing.

7.9 Treatment Assignment

Subjects who are deemed eligible for enrollment into the trial will be randomized to the experimental arm (IRd) vs. the control arm (single-agent lenalidomide) in a 1:1 ratio. Two factors will be considered during randomization:

- a. Level of overall response including transplant from the pre-induction level of disease; response is assessed at study screening 3 months following initiation of lenalidomide maintenance at the time of screening for this protocol:
 - ii. <VGPR
 - iii. ≥VGPR
- 2) Risk Factors at the time of diagnosis
 - iv. At least one of the following poor prognostic risk factors:
 1. del-13 (by karyotyping)
 2. hypodiploidy (by karyotyping)
 3. (4;14) (by FISH)
 4. t(14;16) (by FISH)
 5. t(14;20) (by FISH)
 6. del17p (by FISH)
 7. 1q21 gain (by FISH)
 - v. No risk factors

7.10 Termination of Treatment and/or Study Participation

Patients will be informed that they have the right to withdraw from the study at any time for any reason, without prejudice to their medical care. The investigator also has the right to withdraw patients from the study for any of the following reasons:

- Adverse event
- Protocol violation / subject non-compliance
- Lost to follow-up
- Progressive disease
- Study terminated
- Subject no longer consents to participate in the study
- Pregnancy or suspected pregnancy
- Delay in treatment >21 days due to unrecovered toxicity unless treating investigator considers continued therapy to be in the subject's best interest and approval is granted by the Lead Principle Investigator
- Other

The Lead Principal Investigator must be contacted to discuss any impending discontinuation of a study subject/patient prior to withdrawal from the study. If withdrawal occurs prior to discussion with the Lead Principal Investigator, they must be notified within 24 hours via email with a copy to the University of Chicago CRA.

If the reason for withdrawal is the occurrence of an AE, the subject will be followed until such events resolve, stabilize, and, according to the Treating Investigator's judgment, there is no need of further follow-up. The reason for withdrawal from the study will be documented in the case report form.

At the time of withdrawal, all study procedures outlined for the End of Study visit should be completed. The primary reason for patient's withdrawal from the study should be recorded in the source documents and CRF.

8. STATISTICAL AND QUANTITATIVE ANALYSES

8.1 Statistical Methods

A total of 60 patients will be enrolled in a 1:1 ratio stratified according to level of response (<VGPR vs \geq VGPR) and presence or absence of at least one poor prognostic risk factor (Yes to at least one cytogenetic risk factor including del-13 or hypodiploidy by karyotyping, or any of t(4;14), t(14;16), t(14;2), del17p, 1q21 gain by FISH. The primary objective of this study is to compare the rate of MRD at 12 months between the two arms. Because this is a proof of concept trial rather than a confirmatory trial, the comparison will be made using one-sided test at 80% power and at most 10% type I error. The outcome will be considered promising and warrant evaluation with phase III trial if MRD negative disease is 20% higher in the experimental arm vs. the control arm. This assumption is based on the following data:

- 1) While it is well established that CR rate may increase over time post-transplant, even without any maintenance (in the IFM study, at randomization to lenalidomide maintenance or placebo 5% and 8% of patients were in CR, but ultimately 29% and 27%, respectively achieved CR; Attal et al, N Eng J Med, 2012), the conversion to CR on lenalidomide maintenance in patients with established persistent measurable disease is expected to be less than 5%
- 2) CR rate to lenalidomide alone is estimated < 5% in newly diagnosed myeloma (Rajkumar et al, Blood 2005).
- 3) While there is not published data on the rate of conversion from less than MRD-negative to MRD-negative disease while on lenalidomide maintenance, it is estimated that only a small proportion of patients on lenalidomide arm (which we estimate to be < 5% and/or not to be clinically significant) will convert to MRD-negative status because of delayed effect of transplant and/or lenalidomide treatment.
- 4) Based on experience from the CRd trial ([name] et al, ASCO 2013), approximately 20% of patients have a potential to convert from less than MRD-negative to MRD-negative disease between 8 and 20 months (1-year) of the CRd treatment.

Together, these observations provided rationale for 12 months of duration of treatment and statistical design: an increase of the rate of MRD-negative disease by 20% - 28% in the experimental arm versus control arm was used for calculation of sample size (as for example 26.7 % rate in the experimental arm and 5% in control arm).

In addition, Kaplan-Meier analysis of PFS will be conducted at time points with 95% confidence intervals with Cox proportional hazard regression models (exploratory). For these secondary analyses, conventional, p-values from statistical tests at or below 5% (two-sided) will be considered significant.

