3.2 Secondary Endpoints

- The assessment of other measures of response including rate of VGPR, CR, sCR
- The assessment of duration of MRD-negative disease
- Estimates of PFS and OS
- Estimate of correlation between MRD status and PFS
- The assessment of safety and tolerability of IRd arm compared to R arm

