8.1.1 Determination of Sample Size

A total of 60 patients (30 per arm) is based on the assumption that the rate of MRD negative disease that is approximately 20% higher in the experimental arm vs. the control arm will be considered promising for further evaluation. Because this is a proof of concept phase II randomized trial rather than a confirmatory trial, the comparison will be made using a one-sided test at 80 % power and at most 10% type I error. Table 8.1 below shows the detectable difference depending on the control rate. Boldfaced figures are values assumed most likely based on the literature and previous studies. Calculations are based on a Cochran-Mantel-Haenszel test with continuity correction.

Table 8-1 Detectable increases in the rate of MRD with 80 %power (one-sided $\alpha=0.10$)

Control Arm	Experimental Arm	Difference
2.5%	21.8 %	19.3 %
5.0%	26.7 %	21.7 %
10.0%	35.5 %	25.5%
15.0%	42.4%	27.4%
20.0%	48.1 %	28.1 %

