8.1.6 Efficacy Analysis

The primary objective of this study is to compare the rate of MRD at 12 months between the two arms. Because this is a proof of concept trial rather than a confirmatory trial, the comparison will be made using a one sided test at the 10% significance level. This comparison will be performed using (i) a chi-square or Fisher's exact test comparing the two treatment arms, and (ii) a Cochran Mantel-Haenszel (CMH) test stratified by VGPR status and risk factors vs. no risk factors. We anticipate 20-30% of pts will be high risk and 20-40% will be in less than a VGPR at study entry. Therefore, in the event of small stratum sizes (<5 per stratum in either treatment arm), we will conduct an exact logistic regression analysis in place of the CMH test (Hirji, Mehta, and Patel, et al., 1987).

Secondary objectives include the overall response rate, defined as at least a partial response to therapy (>PR), at least VGPR (>VGPR) and at least nCR rate (>nCR), CR, and sCR rates, time to progression, duration of response, and progression-free and overall survival. The rate of overall response will be reported along with its exact 95% binomial confidence interval. Time to event endpoints will be estimated using the product-limit method of Kaplan and Meier. Follow-

up time for these endpoints will be calculated from the date of randomization. For time to progression, patients that do not experience progression during follow-up will be censored on the date of their last clinical examination. Duration of response will be assessed conditional upon achieving at least a partial response. Follow-up time for this endpoint will be calculated from the date of the clinical examination, which confirmed the response, until the date of disease progression, or censoring at the date of last clinical follow-up. For progression-free survival, follow-up time will continue from the date of randomization until the date of documented disease progression or death. Patients who do not reach either milestone during follow-up will be censored on their date of last clinical assessment.

Correlative biomarkers will be assessed for association with response in the experimental arm using nonparametric tests given the relatively small number of responders anticipated (20%). A Wilcoxon rank-sum test will be used to compare baseline (pre-treatment) biomarker levels in the responders vs. non-responders.

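### The exploratory PFS Cox model, judged at two-sided 5%, names neither randomisation factor, although the MRD analysis uses both; they should be pre-specified as covariates (minor)

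*Combined protocol and SAP*

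**What the plan says.** Section 8.1 sets the allocation: "A total of 60 patients will be enrolled in a 1:1 ratio stratified according to level of response" and by presence of at least one cytogenetic risk factor. Sections 4.1, 7.9 and 8.1.2 repeat this.

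The primary MRD comparison uses both factors. Section 8.1.6 lists an unstratified chi-square or Fisher test and "a Cochran Mantel-Haenszel (CMH) test stratified by VGPR status and risk factors vs. no risk factors", with exact logistic regression if strata are small.

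For PFS, section 8.1 plans that "Kaplan-Meier analysis of PFS will be conducted at time points with 95% confidence intervals with Cox proportional hazard regression models (exploratory". It adds that for these secondary analyses "p-values from statistical tests at or below 5% (two-sided) will be considered significant". It names no covariate or stratum, and it does not say that the models hold treatment alone.

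For the other time-to-event endpoints, section 8.1.6 says "Time to event endpoints will be estimated using the product-limit method of Kaplan and Meier". No Cox model or log-rank test is attached to OS or time to progression, and section 3.2 words the endpoint as "Estimates of PFS and OS".

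The one covariate-adjustment rule in the plan (Populations for Analysis) concerns imbalance in patients who enter as MFC-negative but NGS-positive, for the MRD endpoint. It does not reach PFS.

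**The concern.** The factors were chosen for stratification because they are expected to affect outcome. Section 8.1 itself labels the cytogenetic factors as poor prognostic ones, and section 1.9 describes patients with residual disease who are not in CR as at higher risk of earlier relapse.

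Stratified allocation balances such factors between arms, so the treatment estimate varies less from trial to trial than a treatment-only model assumes. The model's standard error is then too large for its own estimate, and the test rejects too rarely. Separately, a Cox model that omits prognostic factors estimates a marginal hazard ratio, which lies nearer 1 than the ratio within risk groups.

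PFS is a secondary objective and the outcome for which section 1.9 uses MRD as a surrogate, so readers planning a phase III trial will look at this hazard ratio. Leaving the covariates open also means that the model could be chosen after the events are seen.

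**Working it through.** **Plan's own figures.** The documents give no event count, hazard ratio or power for PFS. The only power figures are in Table 8-1, for MRD: "one-sided test at 80 % power and at most 10% type I error", for example "26.7 % rate in the experimental arm and 5% in control arm". With 30 per arm and one-sided alpha 0.10, exact binomial power of the continuity-corrected chi-square (or Fisher) test is 0.799 to 0.801 in all five rows, so the table reproduces. It does not bear on PFS.

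**Inputs from the documents.** 60 patients, 1:1; two binary factors, so four cells; high risk 20-30% and below VGPR 20-40% (8.1.6); 12 months of treatment plus 2 years of follow-up (4.2); two-sided 5% (8.1).

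**Assumed, not in the documents.** Prevalences of 25% and 30% (inside the plan's ranges), exponential PFS, treatment HR 0.5, the reference median PFS, and the prognostic HRs of the two factors. Allocation was simulated as 1:1 within stratum, and tests are Wald at 1.96.

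- Setting A: censoring uniform over 24-36 months, reference median 30 or 60 months, 4,000 trials per row. Monte Carlo SE is √(0.05×0.95/4000) = 0.34 points for error and √(0.4×0.6/4000) = 0.77 points for power.
- Setting B: censoring at 36 months, control low-risk median 40 months, 2,000 to 3,000 trials per run. Ranges are over repeated runs.

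| Setting | Factor HRs | Type I error %, treatment only | Type I error %, adjusted | Power %, treatment only | Power %, adjusted |
|---|---|---|---|---|---|
| A, 30 mo | 1 / 1 | 3.8 | 4.7 | 36.7 | 38.3 |
| A, 30 mo | 1.5 / 1.5 | 4.6 | 5.5 | 40.8 | 43.5 |
| A, 30 mo | 2 / 1.5 | 4.2 | 5.8 | 40.6 | 44.6 |
| A, 30 mo | 2.5 / 2 | 2.7 | 4.9 | 40.2 | 48.9 |
| A, 60 mo | 1 / 1 | 4.3 | 4.8 | 18.9 | 20.1 |
| A, 60 mo | 1.5 / 1.5 | 4.5 | 5.6 | 24.7 | 27.0 |
| A, 60 mo | 2 / 1.5 | 4.1 | 5.1 | 25.2 | 27.9 |
| A, 60 mo | 2.5 / 2 | 3.1 | 4.6 | 26.8 | 33.1 |
| B | 1 / 1 | 5.3 | 5.8 | 34 | 35 |
| B | 2.5 / 1.5 | 3.8-4.4 | 5.5-6.1 | 36-40 | 44-46 |
| B | 4 / 2 | 2.5-3.0 | 5.3-6.1 | 33-34 | 49 |

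Adjusted means Cox with treatment and both factors as main effects.

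**Reading the error column.** With non-prognostic factors the treatment-only error already ranged from 3.8 to 5.3%. The 4.1-4.6% seen with moderate factors is therefore not clearly distinguishable from that baseline. Only strong factors (2.5/2 or 4/2) give a plain departure.

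**Mechanism.** Under the null in setting B, the mean model SE against the empirical SD was 0.326 against 0.298 (HRs 4/2) and 0.341 against 0.329 (2.5/1.5). The effective critical values are 1.96×0.326/0.298 = 2.14 and 1.96×0.341/0.329 = 2.03, which imply two-sided errors of about 3.2% and 4.2%. This is close to the simulated values.

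**Estimate.** The true log HR is ln 0.5 = -0.69. In setting B the mean log HR with 2.5/1.5 was -0.67 unadjusted and -0.74 adjusted. With 4/2 it was -0.58 to -0.59 unadjusted and -0.72 adjusted.

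**Main effects or strata.** Assuming the factors are independent, the smallest cell is expected to hold 60×0.2×0.2 = 2.4 to 60×0.3×0.4 = 7.2 patients. In setting A, a Cox model stratified by the four cells changed power by only -0.5 to +4.8 points.

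**Ceiling.** Events needed for 80% power at HR 0.5: 4×(1.96+0.84)²/(ln 0.5)² ≈ 65.3, so 66, which is more than the 60 patients enrolled.

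**The case against.** The plan is silent rather than wrong. It says models, in the plural, and labels them exploratory, so an analyst could include the factors without departing from it. The phase III trigger is the MRD difference, not PFS. Power at HR 0.5 stays below 50% with or without adjustment. All of this stands, and it makes the point a minor one. It does not remove it, because the same paragraph of section 8.1 attaches a significance threshold to a model whose covariates are left open.

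Four stronger readings are tempting, and the documents or the figures do not support them.

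- A reader might infer that OS and time to progression are also tested without the factors. Section 8.1.6 plans only Kaplan-Meier estimates for them, so no planned test or hazard ratio exists to be conservative.
- A reader might infer that adjustment is free. Adjusted type I error ran at 4.6-6.1%, so part of the power gain comes from restoring, and sometimes slightly exceeding, the nominal level. A likelihood-ratio test does not cure this: in null runs it rejected slightly more often than Wald (for example 5.9% against 5.5%, and 6.1% against 5.9%).
- A reader might infer that the reported intervals would be too wide and that adjustment narrows them. The treatment-only SE does overstate that estimate's spread, but adjustment raises the reported SE slightly: 0.392 to about 0.399 with HRs 2.5/1.5, and 0.364 to 0.375 with 4/2. Root mean squared error around the true log HR also rises, from 0.382 to 0.419 and from 0.348 to 0.393. The power comes from a larger estimate.
- A reader might call the unadjusted estimate biased toward no effect. It targets a different, marginal quantity, and with HRs 2.5/1.5 its mean (-0.67) is nearer -0.69 than the adjusted mean (-0.74). Clear attenuation needs stronger factors.

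**Conclusion.** The point holds as a minor improvement to the PFS analysis. The PFS Cox model does not name the two factors on which patients are randomised, although the primary analysis uses them.

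If the model is fitted with treatment alone, its type I error is about 2.5-4.6% over assumed factor HRs from 1.5/1.5 to 4/2, and only the stronger factors take it clearly below its level. Main-effects adjustment gains about 2-4 points of power at HR 0.5 with moderate factors, about 6-9 with strong ones, and about 15 only under the extreme 4/2 assumption. It lost no power when the factors had no effect (gains of 1 to 2 points).

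These sizes rest on assumed prognostic hazard ratios, PFS medians and treatment effect, none of which the documents give. The direction rests on the protocol's own premise that the factors are prognostic.

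**What to change.** Add one sentence to section 8.1, repeated or cross-referenced in 8.1.6: the PFS hazard ratio comes from a Cox model with treatment, response level (<VGPR vs ≥VGPR) and cytogenetic risk (any listed factor vs none) as main effects, with the treatment-only model as a sensitivity analysis. Use main effects rather than four strata because the smallest cell is expected to hold about 2 to 7 patients. Keep the Kaplan-Meier curves by arm. In the same edit, state whether any test is planned for OS and time to progression.

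The cost is that sentence. Both factors are needed to randomise, so no new data are required. The report should note that, with some 30 events, the adjusted test may run slightly above 5% and the standard error will be marginally larger than in the unadjusted fit.
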